7.1 ASSESSMENT/EVALUATION PLAN

Assessment and Measurement Instruments:

In this study, the data will be collected using the following instruments and measurements methods:

- Electronic Medical Record review:

- 1- For patients in the intervention group (automated geriatric co-management), we will assess the percentage of recommendations that were followed by the surgery team. For example, if automated geriatric co-management recommends consultation with physical therapy perioperatively, we will assess whether the consult has been obtained.
- 2- For patients in both groups, we will assess the adverse surgical events by day 30 following surgery. Adverse surgical event is a composite of surgical complications grade 2 or higher, mortality after surgery, or discharge to any place other than home, or prolonged length of stay (defined as length of stay longer than 75% of the cohort who underwent the same surgical procedure), or readmission to the hospital within 30 days from surgery.

MSKCC's secondary surgical events database in the EMR has been shown to accurately record major postoperative complications within the 30 days after surgery[34].

- 3- to assess sociodemographic characteristics (age, gender, ethnicity),
- 4- to assess routine preoperative blood work (complete blood cell counts, chemistry panel).
- 5- To assess cancer characteristics (stage, receipt and type of neoadjuvant treatment)

- 6-** To assess surgical characteristics (type of surgery: minimally invasive vs open, duration of surgery, intraoperative blood loss, and American Society of Anesthesiologist Physical Status classification)
- **Four Meter Walk Test:** In order to assess functional recovery, the 4-meter walk test will be performed. In the 4-meter walk test, the time that it takes patients to walk 4 meters in their usual pace will be recorded in seconds by the clinical research staff. (This portion will be skipped for patients being seen via telemedicine.)

Assessment and Evaluation Plan

Patients will be screened for study eligibility at the time of attending their surgery appointment at MSKCC for consideration of surgery. The inclusion and exclusion criteria will be reviewed by the clinical research staff firstly to confirm the patients' eligibility status. Once eligibility has been determined and informed consent has been obtained, patients will undergo baseline assessments and subsequently randomization will occur.

There will be two study visits for patients in both groups; baseline or pre-op visit (1st) and the 2nd visit. Baseline visit occurs at the time of new visit by the surgery team, or in the case that two months has passed since baseline, at the pre-op visit. 2nd visit occurs at the time of follow up after hospital discharge by the surgeons. Both baseline and 2nd visit may be conducted via telemedicine if preferred.

Baseline Study Visit/Pre-op Visit: In this visit, following assessments will be performed.

- The 4-Meter Walktest.
- Sociodemographic characteristics.
- eRFA completion per routine care

2nd Study visit: In this visit, following assessment will be performed.

- The 4-Meter Walktest.
- eRFA completion per routine care

Study participant follow up:

Thirty days after surgery:

- Collection of adverse surgical events (grade 2 or more complications, length of stay, readmission, disposition plan), surgery and cancer characteristics, and preoperative blood work results.

	Screening & Baseline study visit	Pre-operative visit	2 nd study visit (within 2 weeks of surgery)	30 Day post-surgery follow up
--	----------------------------------	---------------------	---	-------------------------------

Informed consent	✓			
------------------	---	--	--	--

Eligibility determination	✓			
Randomization	✓ (if proceeding with surgery in 2 months)	✓ (if two months have passed by from baseline visit)		
eRFA completion, per SOC	✓	✓ (if two months have passed since baseline visit)	✓	
Automated geriatric co-management program		✓	✓	
In-person geriatric co-management program		✓	✓	
4 MWT	✓	✓ (if two months have passed by from baseline visit)	✓	
Sociodemographic data	✓			
Preoperative lab results				✓
Cancer characteristics				✓
Surgical characteristics				✓
Adverse events				✓

8.0 TOXICITIES/SIDE EFFECTS

There are minimal adverse events or risks associated with participation in this study. Staff will be adequately trained to identify any signs of distress that may be experienced by a patient during the course of their participation in the study.

Burden of Assessment

It is possible that patients may not be able to or willing to do 4-Meter walk test. This test will only be performed if patients are comfortable with them. Study participants will be given contact details of the clinical research staff dedicated to this study in case they have any questions or concerns regarding study.

Patient Identification of Unmet Clinical Needs

If thoracic surgeons and/or other healthcare providers are concerned about the unmet needs of patients before or after surgery, they are encouraged to obtain proper medical and non-medical consultations.

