intervention will be deemed feasible if recommendations are followed for 50 patients. Finally, we will present the distribution of number of recommendations made and followed in the automated geriatric comanagement arm.

Secondary Aims

Effect of the automated geriatric co-management program compared to the in-person geriatric co-management on adverse surgical events.

All between-group comparisons will be by modified intent-to-treat (complete case analysis), with patients analyzed according to randomization, irrespective of whether they were proceeded to automated geriatric co-management or in-person geriatric co-management. To compare, by intervention arm, the proportion of patients with a composite outcome ("adverse surgical event") of either surgical complications grade 2 or higher, or prolonged hospital length of stay, or discharge to another care facility rather than home, or 30-day readmission to the hospital. Prolonged hospital length of stay will be defined as hospital length of stay greater than 75% of the cohort who underwent the similar procedure. We will test the association between intervention arm and adverse surgical event using logistic regression with the randomization stratum as the covariate.

It is plausible that the relative value of in-person vs. automated geriatric *co-management* depends on baseline risk, for instance, it could be that average risk patients are adequately managed by the automated approach, but those at high risk require individualized care. To this end, we will use a logistic regression with adverse surgical event as the outcome, study arm as the predictor, randomization strata as the covariate, and adjust for continuous baseline risk using the MSK-FI, with restricted cubic splines with knots at the tertiles to allow for non-linearity. We will then visualize the risk in both intervention arms across baseline risk to provide an individualized estimate of benefit for a given level of baseline deficit. The MSK-FI is a frailty index defined by ten sets of comorbidities, and one component related to dependency on five activities of daily living. The former will be queried from the institutional database, and the latter is assessed using the bADL and iADL measures on the eRFA.[35]

Effect of the automated geriatric co-management program with in-person geriatric co-management on postoperative functional recovery.

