To compare, by intervention arm, postoperative functional recovery. We will consider postoperative functional recovery as reported by the patient, as well as assessed by the study team during the 2nd study visit. Patient-reported recovery will be measured by three domains reported on both pre and post-operatively: Karnofsky Performance Status, basic activities of daily living, and instrumental activities of daily living.

Clinician-evaluated functional recovery will be assessed through the Timed Up and Go

test and the 4MWT. This analysis will only be done for patients who have completed the assessment during in-person visit with the surgery team. Recovery of Karnofsky Performance status, defined as the same or better Karnofsky Performance status during the 2nd study visit compared to baseline, will be compared between groups using a logistic regression with randomization strata as covariates. Basic activities of daily living, instrumental activities of daily living, Timed up and Go test and 4MWT will be compared between groups by ANCOVA, with baseline score and randomization strata as a covariate.

In the case that patient's surgery occurs after two months of completing the eRFA, either the patient has to complete another eRFA within two months of surgery, which then will be the patient's new preoperative baseline eRFA, or in case of not completing the eRFA, the patient will be excluded from the study.

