We are additionally interested in using the three components, of the patient-reported functional recovery in three categories: complete recovery (defined as all three post-operative measurement score being greater than or equal to the pre-operative measurement score), partial recovery (defined as at least one, but not all three, post-operative measurement scores being greater than or equal to the pre-operative measurement score), or no recovery (defined as none of the post-operative measurement scores being greater than or equal to the pre-operative measurement score). Similarly we will use two components of the clinician-evaluate functional recovery to define three categories: complete recovery (defined as all both post-operative measurement score being greater than or equal to within 10% of the pre-operative measurement score), partial recovery (defined as at least one, but not both, post-operative measurement scores being greater than or equal to within 10% of the pre-operative measurement score), or no recovery (defined as neither of the post-operative measurement scores being greater than or equal to within 10% of the pre-operative measurement score). We will test the association between intervention arm and degree of recovery by using ordinal regression with randomization strata as covariates.

As it is likewise plausible that the relative value of in-person vs. automated geriatric co-management depends on baseline risk, we will repeat the analysis described above, related to baseline risk, for the outcomes of patient-reported functional recovery and clinician-assessed functional recovery.

Sample size

With a null hypothesis of 55% and the alternative hypothesis of 70% of patients with recommendations followed, and a one-sided α of 5% and a power of 85%, we require 77 eligible patients to be accrued in the automated geriatric co-management arm for a two-stage Simon minimax design. We expect about 25% of patients to be excluded for the primary aim due to no impairment (5%) or crossover to the in-person

geriatric comanagement arm (20%) suggesting a total accrual close to 100 per group.

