Assuming a correlation of 0.5 between baseline and follow-up, and a standard deviation of 1.8 (as seen in our preliminary dataset for the basic activities of daily living, the score of which ranges from 0 to 14), with ~95 patients per arm (after an estimated 5% loss of patients due to drop out), the power for various effect sizes for our continuous secondary endpoints when analyzed using ANCOVA are shown in the table, where it can be seen that we have high power to detect small differences between groups. Sensitivity analyses will be conducted where missing outcome data will be imputed by Multiple Imputation using Chained Equations.

Difference between groups	Power
0.5	60%
0.67	84%
0.8	94%

In 2017, the surgical services had completed surgical procedures on more than 5000 patients aged 65 or older with a hospital length of stay of 2 days or longer. Therefore, we expect to enroll the 200 patients for our study in less than two-years. We expect most patients to be older (75+) but to ensure that younger patients are not overly represented, we will cease accrual of patients 65 – 74 after 60 are accrued (i.e. 30%).

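### A patient who walked at baseline but physically cannot do the 4-meter walk at the second visit drops out of clinician-evaluated recovery instead of counting as not recovered

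*Combined protocol and SAP*

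**What the plan says.** Section 8.0 (Burden of Assessment) says of the 4MWT: "It is possible that patients may not be able to or willing to do 4-Meter walk test". It continues: "This test will only be performed if patients are comfortable with them". Inability and unwillingness share one sentence, and no section asks staff to record which applied.

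Section 11.0 (Secondary Aims) sets the general population: "All between-group comparisons will be by modified intent-to-treat (complete case analysis), with patients analyzed according to randomization". For the clinician-evaluated measures, TUG and 4MWT, it adds: "This analysis will only be done for patients who have completed the assessment during in-person visit with the surgery team". The continuous analysis is stated as: "Timed up and Go test and 4MWT will be compared between groups by ANCOVA, with baseline score and randomization strata as a covariate".

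The three-level clinician-evaluated outcome also compares measured scores. Its lowest level reads: "no recovery (defined as neither of the post-operative measurement scores being greater than or equal to within 10% of the pre-operative measurement score". No section gives a value, rank or category to a patient who attends but cannot do the test.

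Under Sample size, Section 11.0 provides sensitivity analyses in which "missing outcome data will be imputed by Multiple Imputation using Chained Equations", with no rule for inability. Figure 2 records TUG in three time bands, the worst being 20 seconds or more, and does not say where a patient who cannot perform it belongs. Sections 3.1 and 7.1 omit TUG and 4MWT at telemedicine visits.

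**The concern.** A walk that could be done before surgery and cannot be done after it is an observed poor result, not an unknown one. Care given after randomization can influence it. If such patients are removed, recovery is estimated among those well enough to be tested, and the two arms' tested groups may no longer be comparable.

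The trial is meant to inform whether the automated program does as well as in-person co-management, and a later, larger study is planned from it. A loss of contrast between arms would make the two look more alike than they are, so the point estimates matter even though the secondary aims are preliminary.

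**Working it through.** **1. Follow one patient through the text.** The patient does the 4MWT at baseline, attends visit 2 in person and physically cannot do it.
- Section 8.0: the test is not performed.
- Section 11.0, restriction to completers: the patient has not completed the assessment and is outside the analysis set.
- Section 11.0, complete-case rule: there is no post-operative time, so the ANCOVA cannot use the patient.
- Recovery categories: the lowest level could be read as covering someone who fails to reach the threshold, but the completer restriction applies first.
- Imputation: the patient is pooled with those who declined, were seen remotely or dropped out, and is given a walking time.

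**2. The plan's only related figure.** The power table uses SD 1.8 (bADL), correlation 0.5 and 95 per arm. Alpha is not stated there; I assume two-sided 5%.
- Adjusted SD = 1.8 × √(1 − 0.5²) = 1.559. Standard error = 1.559 × √(2/95) = 0.226.
- Power = Φ(difference/0.226 − 1.96) = 59.9%, 84.2% and 94.3% for 0.5, 0.67 and 0.8.

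The plan states 60%, 84% and 94%, so the table reproduces. It concerns bADL and does not speak to how inability is handled.

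**3. Recovery on the 4MWT component (assumed rates).** Let r be the share of tested patients who recover and u the share unable. Completers show r; counting the unable as not recovered gives r × (1 − u).

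| r, both arms | u, arm A vs B | Completers | All in-person attendees | Gap hidden |
|---|---|---|---|---|
| 50% | 5% vs 10% | 50% vs 50% | 47.5% vs 45.0% | 2.5 points |
| 50% | 5% vs 15% | 50% vs 50% | 47.5% vs 42.5% | 5 points |
| 60% | 5% vs 10% | 60% vs 60% | 57% vs 54% | 3 points |
| 60% | 5% vs 20% | 60% vs 60% | 57% vs 48% | 9 points |

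Within an arm, the completer figure is too high by r × u: 2.5 points at r = 50%, u = 5%, and 7.5 points at u = 15%.

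**4. Direction.** The completer contrast (A minus B) differs from the full one by r_A·u_A − r_B·u_B, so the sign depends on both quantities. Take A with r = 50%, u = 20%, and B with r = 70%, u = 15%. Then 0.50 × 0.20 − 0.70 × 0.15 = −0.005. The completer analysis favours B by half a point although A has more patients unable.

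**5. Continuous score (assumed model).** Suppose ability is normal with unit SD, patients below a common threshold c cannot do the test, and the arms truly differ by 0.67/1.8 = 0.372 SD (a size borrowed from the bADL table). With f(c) = φ(c)/(1 − Φ(c)), the difference among completers is f(c) − f(c + 0.372) + 0.372.

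| Unable, better arm | Unable, worse arm | Difference among completers | Retained |
|---|---|---|---|
| 5% | 10.2% | 0.283 SD | 76% |
| 10% | 18.2% | 0.245 SD | 66% |
| 15% | 25.3% | 0.218 SD | 59% |

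**The case against.** The completer sentence in Section 11.0 ends by referring to the in-person visit, and its evident purpose is to set telemedicine patients aside. It was probably not written as a rule for attendees who cannot walk. That is fair as to intent, but together with the complete-case rule its effect is still to remove them.

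Section 8.0 names only the 4MWT. Nothing makes TUG optional, and its open-ended top band might be where an unable patient is coded. A reader might infer that both tests lose these patients; the documents do not show that for TUG, only that its coding is unstated.

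A reader might also infer that these patients vanish from functional recovery altogether. They do not. KPS, bADL and iADL need no walk test, bADL asks about walking inside and outside the house, and these measures have their own ordinal outcome. This softens the consequence but does not repair the separate clinician-evaluated endpoint.

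On imputation, the variables are not listed, and a model that includes post-operative bADL or KPS could predict slow times for these patients. It would still assign a measurable time, normally under a missing-at-random assumption.

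Finally, the effects illustrated are small for this trial. For 47.5% versus 42.5% with 95 per arm, the standard error is √[(0.475 × 0.525 + 0.425 × 0.575)/95] = 0.072, so power at two-sided 5% is about Φ(0.05/0.072 − 1.96), or 10%. This stands, but the aim is preliminary estimation, where bias matters whether or not a test would be significant. The case report forms are not in the documents, so a reason may already be collected.

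**Conclusion.** The point holds for the 4MWT. As written, a patient tested at baseline who attends visit 2 in person and physically cannot do the test is excluded instead of being counted as not recovered, and the sensitivity analysis does not separate this case. For TUG it is a possibility, because coding of inability is not stated.

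The exclusion tends to overstate clinician-evaluated recovery. It can distort or shrink the arm comparison if inability differs by arm: 2.5 to 9 points hidden on the 4MWT component, or 59% to 76% of a 0.372 SD difference retained, under the assumed rates and model above. The documents give no inability rates, so these are illustrations.

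A reader might conclude that the comparison is necessarily biased towards the arm with more patients unable. The documents do not support that: the sign also depends on recovery among those tested, as step 4 shows. Nor is every untested patient a poor outcome, since some will decline or be seen remotely.

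The endpoint is secondary. The primary feasibility result, its interim rule and its sample size are unaffected. The change is worth making because the reason for a missed test may be hard to reconstruct later.

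**What to change.** - **Record.** At each in-person visit, code 4MWT and TUG separately as completed, physically unable, declined, or not done for logistics. Keep telemedicine as its own code.
- **Ordinal analysis (Section 11.0).** Where the test was done at baseline, score physically unable at visit 2 as not recovered on that component. A patient recovered on the other component is then partial, not no recovery. Amend the completer restriction so that it does not remove these patients.
- **Report.** Tabulate inability by arm for each test.
- **Missing data.** Treat only declined, logistic and telemedicine cases as missing, and impute only those.
- **Continuous analysis.** Keep the ANCOVA on measured times, labelled as conditional on being able to do the test. Add a sensitivity analysis that ranks unable worst; a rank-based ANCOVA is one option, and other methods are defensible.

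The cost is one data field per test and a paragraph in Section 11.0. The rank-based result is less direct to read than a difference in seconds, which is why both should be shown.

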9.0 PRIMARY OUTCOMES

	Baseline study visit	Preoperative visit (if two months have passed by from baseline study visit)	2 nd study visit	30-day post-surgery follow up
eRFA (including Karnosky Performance Status, basic Activities of Daily Living, instrumental Activities of Daily Living, Timed-up-and-Go test)	✓	✓	✓	
4 MWT	✓	✓	✓	
Sociodemographic characteristics	✓			
Preoperative lab results				✓
Cancer characteristics				✓
Surgical characteristics				✓
Adverse events				✓
Hospital Length of Stay				✓
Discharge/Disposition location				✓
30-day readmission to hospital				✓
Number of geriatric recommendations followed				✓

10.1 CRITERIA FOR REMOVAL FROM STUDY

Patients will have completed their participation in this study after the 30-day post-surgery follow-up or the 2nd study visit, whichever occurs later, and will be considered off-study.

Participants will be removed from the study if:

- ✓ He/she chooses to withdraw consent for continued participation at any time
- ✓ The participant reports intolerable distress due to study participation
- ✓ He/she becomes ineligible for study participation as designated by the inclusion/exclusion criteria

11.0 BIOSTATISTICS

This is a prospective, randomized trial of automated geriatric co-management in patients presenting to the surgery clinic for surgery compared with standard in-person geriatric co-management. Patients will be randomized 1:1 to either arm according to section 12.2.

Primary Aims

Feasibility of the automated geriatric co-management program in the care of geriatric oncology patients.

Among patients randomized to the automated geriatric arm of the study we will calculate the proportion of patients for whom at least half of the recommendations made were followed by the surgical team. **Our program will be deemed feasible if at least 50% of recommendations are followed in at least 70% of patients with impairments.** We based our cutoff based on multiple studies. A study done on surgeons' attitude toward assessment and management of older cancer patients, Ghignone et al[1], showed that only 6.4% of surgeons use geriatric assessment in their daily practice and only 36% collaborate with geriatricians in some form. Studies on geriatric comanagement of older adults who are receiving chemotherapy also showed that the pickup rate of interventions by the medical oncologists is around 35%[2]. Given these findings, we hypothesized that a more than 50% adoption of recommendations would be a reasonable rate for then refining the intervention and conducting an R01 study in the future.

We will first report the number of patients that were randomized to the automated geriatric comanagement arm but were subsequently referred to the geriatric in-person comanagement arm and report the distribution of recommendations made for these crossover patients. We will analyze 77 patients with at least one eRFA impairment who adhere to the automated geriatric comanagement arm and are not seen by geriatrics service for preoperative evaluation (crossover). In all analyses for the primary aim, we will exclude those who do not have any baseline impairment or have crossed over to the in-person geriatric comanagement arm. An interim analysis will be conducted after 38 patients are accrued. If 50% of recommendations were followed for 21 or fewer patients, the trial will be stopped for futility. Otherwise, accrual of 77 eligible patients will be completed, after which accrual will be closed to additional patients. The

intervention will be deemed feasible if recommendations are followed for 50 patients. Finally, we will present the distribution of number of recommendations made and followed in the automated geriatric comanagement arm.

Secondary Aims

Effect of the automated geriatric co-management program compared to the in-person geriatric co-management on adverse surgical events.

All between-group comparisons will be by modified intent-to-treat (complete case analysis), with patients analyzed according to randomization, irrespective of whether they were proceeded to automated geriatric co-management or in-person geriatric co-management. To compare, by intervention arm, the proportion of patients with a composite outcome ("adverse surgical event") of either surgical complications grade 2 or higher, or prolonged hospital length of stay, or discharge to another care facility rather than home, or 30-day readmission to the hospital. Prolonged hospital length of stay will be defined as hospital length of stay greater than 75% of the cohort who underwent the similar procedure. We will test the association between intervention arm and adverse surgical event using logistic regression with the randomization stratum as the covariate.

It is plausible that the relative value of in-person vs. automated geriatric *co-management* depends on baseline risk, for instance, it could be that average risk patients are adequately managed by the automated approach, but those at high risk require individualized care. To this end, we will use a logistic regression with adverse surgical event as the outcome, study arm as the predictor, randomization strata as the covariate, and adjust for continuous baseline risk using the MSK-FI, with restricted cubic splines with knots at the tertiles to allow for non-linearity. We will then visualize the risk in both intervention arms across baseline risk to provide an individualized estimate of benefit for a given level of baseline deficit. The MSK-FI is a frailty index defined by ten sets of comorbidities, and one component related to dependency on five activities of daily living. The former will be queried from the institutional database, and the latter is assessed using the bADL and iADL measures on the eRFA.[35]

Effect of the automated geriatric co-management program with in-person geriatric co-management on postoperative functional recovery.

To compare, by intervention arm, postoperative functional recovery. We will consider postoperative functional recovery as reported by the patient, as well as assessed by the study team during the 2nd study visit. Patient-reported recovery will be measured by three domains reported on both pre and post-operatively: Karnofsky Performance Status, basic activities of daily living, and instrumental activities of daily living.

Clinician-evaluated functional recovery will be assessed through the Timed Up and Go

test and the 4MWT. This analysis will only be done for patients who have completed the assessment during in-person visit with the surgery team. Recovery of Karnofsky Performance status, defined as the same or better Karnofsky Performance status during the 2nd study visit compared to baseline, will be compared between groups using a logistic regression with randomization strata as covariates. Basic activities of daily living, instrumental activities of daily living, Timed up and Go test and 4MWT will be compared between groups by ANCOVA, with baseline score and randomization strata as a covariate.

In the case that patient's surgery occurs after two months of completing the eRFA, either the patient has to complete another eRFA within two months of surgery, which then will be the patient's new preoperative baseline eRFA, or in case of not completing the eRFA, the patient will be excluded from the study.

We are additionally interested in using the three components, of the patient-reported functional recovery in three categories: complete recovery (defined as all three post-operative measurement score being greater than or equal to the pre-operative measurement score), partial recovery (defined as at least one, but not all three, post-operative measurement scores being greater than or equal to the pre-operative measurement score), or no recovery (defined as none of the post-operative measurement scores being greater than or equal to the pre-operative measurement score). Similarly we will use two components of the clinician-evaluate functional recovery to define three categories: complete recovery (defined as all both post-operative measurement score being greater than or equal to within 10% of the pre-operative measurement score), partial recovery (defined as at least one, but not both, post-operative measurement scores being greater than or equal to within 10% of the pre-operative measurement score), or no recovery (defined as neither of the post-operative measurement scores being greater than or equal to within 10% of the pre-operative measurement score). We will test the association between intervention arm and degree of recovery by using ordinal regression with randomization strata as covariates.

As it is likewise plausible that the relative value of in-person vs. automated geriatric co-management depends on baseline risk, we will repeat the analysis described above, related to baseline risk, for the outcomes of patient-reported functional recovery and clinician-assessed functional recovery.

Sample size

With a null hypothesis of 55% and the alternative hypothesis of 70% of patients with recommendations followed, and a one-sided α of 5% and a power of 85%, we require 77 eligible patients to be accrued in the automated geriatric co-management arm for a two-stage Simon minimax design. We expect about 25% of patients to be excluded for the primary aim due to no impairment (5%) or crossover to the in-person

geriatric comanagement arm (20%) suggesting a total accrual close to 100 per group.

Assuming a correlation of 0.5 between baseline and follow-up, and a standard deviation of 1.8 (as seen in our preliminary dataset for the basic activities of daily living, the score of which ranges from 0 to 14), with ~95 patients per arm (after an estimated 5% loss of patients due to drop out), the power for various effect sizes for our continuous secondary endpoints when analyzed using ANCOVA are shown in the table, where it can be seen that we have high power to detect small differences between groups. Sensitivity analyses will be conducted where missing outcome data will be imputed by Multiple Imputation using Chained Equations.

Difference between groups	Power
0.5	60%
0.67	84%
0.8	94%

In 2017, the surgical services had completed surgical procedures on more than 5000 patients aged 65 or older with a hospital length of stay of 2 days or longer. Therefore, we expect to enroll the 200 patients for our study in less than two-years. We expect most patients to be older (75+) but to ensure that younger patients are not overly represented, we will cease accrual of patients 65 – 74 after 60 are accrued (i.e. 30%).

